- The number and percentage of participants in each of the six categories on Day 90 will be tabulated, and the adjusted summary OR of the active versus control group will be estimated with a 95% CI, using a proportional odds model as described above.

Sensitivity Analyses:

- In addition to the adjusted summary OR, the unadjusted summary OR with 95% CI will be shown (estimated using a proportional odds model without adjustment for disease severity). In the case that the adjusted OR differs substantially from the unadjusted OR, the reason for the deviation will be explored.
- The primary comparison will be repeated after excluding participants who did not receive any of the investigational agent/placebo (modified intention-to-treat).

- To supplement the overall summary odds ratio for the 6-category *recovery* outcome, each dichotomized definition of improvement that can be formulated from the components of the ordinal outcomes will be considered separately; for example, treatment groups will be compared for the proportions of participants in category 1 on Day 90; for the proportions in categories 1 or 2 (“best two categories”), in categories 1-3, etc. Proportions will be tabulated, and odds ratios for active versus control groups will be estimated with 2-sided 95% CIs using logistic regression models. These analyses need to be interpreted with caution, because they are not adjusted for inflation of type I error due to multiple comparisons.
 - The validity of the proportional odds assumption for the primary endpoint will be assessed by testing for heterogeneity in the log ORs (for the treatment effect) across the dichotomized cumulative ordered categories in the corresponding logistic regression model and across the stratification covariate (partial proportional odds model, test for “unequal slopes”), as described in section 3.
- **Subgroup analyses** will be carried out for the primary outcome. The goal is to determine whether the treatment effect differs across subgroups, and to aid the DSMB in considerations on whether there are safety concerns in specific subgroups. Principles for subgroup analyses are described in section 8.5; here, subgroup analyses are based on the proportional odds models. In particular, heterogeneity of the treatment effect by disease severity at baseline will be assessed.

8.3 Key Secondary Outcomes

The TESICO protocol identifies four key secondary outcomes (protocol section 11.2):

- **Mortality** through Day 90 is a key secondary outcome; analyses are described in section 7.1. In addition, interim monitoring boundaries are based on time to death (rather than the primary ordinal endpoint of *recovery*). Corresponding analyses are described in section 10.2.
- To supplement the separate analyses of *recovery at day 90* and *time to death*, a composite endpoint that considers the number of days at home off oxygen and the time to death (instead of just survival status at day 90) as well as the other categories of the primary ordinal recovery outcome will be analyzed jointly using the “**win ratio**” method.⁸ (This analysis will be performed when the trial is completed).

The win ratio will be calculated using the matched pairs method described in Pocock (2012).⁸ Pairs will be formed by matching participants by disease severity (requiring invasive mechanical ventilation or ECMO), and by ranking the participants in each treatment group according to a risk score, described in section 13.1, and pairing the participants in groups A (here referring to the investigational drug) and B (referring to control) with equal ranks. Details are given below.

- If both treatment groups have the same number of observations, the win ratio is calculated as follows:

Step 1: Calculate the risk score for all participants, and order participants by the risk score in each treatment group. If needed, break ties at random. Each participant forms a “matched pair” with the participant of equal rank order in the other treatment group.

Step 2: For each pair, determine whether the participant in group A wins, loses, or neither:

- a. Compare pairs for *time to death*, for all pairs where one or both participants died.

If the participant in group A died, wins and losses are computed as follows:

- If the matched participant in group B has longer follow-up, then A loses and B wins.
- If the matched participant in group B has shorter follow-up and is alive at the censoring date, then neither group wins.

Repeat for pairs where the participant in group B died.

- b. Compare remaining pairs for category 5 of the primary outcome, *hospitalized for medical care OR in hospice care*

c. Compare remaining pairs for category 4 of the primary outcome, *not hospitalized AND either at home on oxygen OR not at home*

 - Per protocol, the recovery status in the primary ordinal outcome is defined using the “last-off” method, i.e., hospital re-admission, change from home to a higher level of care, or receipt of new supplemental oxygen changes the status to “not recovered”. In contrast, the cited statistical methods for time-to-first-event analyses require that “recovery” is defined as an absorbent state, i.e., once a participant achieved “recovery”, they will not revert to a different state later. Therefore, we will present two analyses:
 - Time to *first* being discharged from the hospital, at home, and off new oxygen.
 - Time to *last* being discharged from the hospital, at home, and off new oxygen; this corresponds to the “last-off” method. Results will have to be interpreted with caution, as the last-off method violates assumptions for the standard time-to-(first)-event analyses.
 - Time to *first* being *discharged from the hospital, at home and off oxygen for 14 consecutive days* will be analyzed to aid in the interpretation of “time to recovery”.
- Status on a 3-category ordinal outcome that includes (a) recovered (alive, at home, and off new oxygen), (b) alive but not recovered, and (c) dead, assessed at Day 90. Here, *new oxygen* is defined as supplemental oxygen above the level that was used prior to COVID-19. Treatment groups will be compared using proportional odds models, stratified by disease severity.

8.4 Other Secondary Outcomes

The protocol defines a number of secondary endpoints in addition to the four key endpoints described in section 8.3 above. These analyses will be carried out for the final report. Selected secondary endpoints may also be analyzed for interim monitoring reports, to help evaluate the safety and efficacy of the investigational agent.

Below, the secondary outcomes from section 4.1.2 of the protocol are cited, with a short description of the analysis methods. For each outcome, the treatment groups will be compared by intention-to-treat, stratified by disease severity at study entry, as described in section 3 under “stratification”.

- Time to discharge from the initial hospitalization. Treatment groups will be compared using time-to-event methods that take into account the competing risk of death, similar to the analyses for time to recovery described in section 8.3.
 - Hospital readmissions will be summarized using methods for recurrent events (i.e. those who are readmitted will re-enter the risk set).⁹
- *Hospital-free days to Day 90* (days alive outside of a short-term acute care hospital up to day 90). For this analysis, the “last-off” method will be used, i.e., days from the latest hospital discharge to day 90 will be counted. A person who dies within 90 days will be assigned a value of -1, consistent with the approach taken in many trials of intensive care-based interventions. We will present the median days by group and test the hypothesis of no difference between arms with a Wilcoxon rank sum test.
 - For interim analyses, only participants who have reached Day 90 (administrative follow-up for those who died) will be included, to avoid bias. Alternatively, the current follow-up time may be used, censored at the time point when the outcome status was last known for participants who were alive.
- A composite of death, clinical organ failure, or serious infection through Days 28 and 90 (see Appendix B). Analyses were described in section 7, under “PSESE”.
- **Time to sustained recovery** through Day 90, defined as being discharged from the index hospitalization, followed by being alive and *home* for 14 consecutive days. (This is the primary endpoint in the ACTIV-3/INSIGHT 014/TICO protocol.) The analyses methods will take into account the competing risk of death, using the Aalen-Johansen method to estimate cumulative incidence functions, and Gray's test and the Fine-Gray method for treatment comparisons.
- Outcomes assessed in other treatment trials of COVID-19 for hospitalized participants in order to facilitate meta analyses and facilitate generation of norms, including an ordinal scale measuring the degree of oxygen support through Day 14, time to discharge from the initial hospitalization, and binary outcomes defined by worsening based on the worst 3 categories of the primary ordinal recovery outcome at day 90. We will try to match the analyses in the other trials, to get results that can be compared. These analyses will not be performed for interim reports to the DSMB, unless requested.

- A composite of cardiovascular events (outcomes listed in items b1, e2 and e3 in [Appendix B](#)) and thromboembolic events (item f2) through Day 28 and Day 90. Time to event methods will be used that take into account the competing risk of death, e.g., Gray's test to compare treatment groups.

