 - The primary analysis to assess whether the effects of aviptadil and remdesivir are **independent** of each other will be conducted in the factorial cohort, by testing for an interaction effect. If there is evidence for an interaction ($p<0.05$), the effect of aviptadil versus placebo will be estimated for those who were randomized to remdesivir, and for those who were randomized to remdesivir-matched placebo. Analyses that will be conducted in the factorial cohort are described in Section 9.

Comment: Additionally, the independence of the effects of aviptadil and remdesivir will also be assessed in subgroup analyses within the aviptadil and remdesivir cohorts. For example, in subgroup analyses for aviptadil versus placebo, heterogeneity of the treatment effects across subgroups by remdesivir use (use at baseline or randomized to remdesivir versus neither) will be assessed by testing for an interaction between treatment and subgroup indicators. The assessment of independence is protected by randomization in the factorial cohort, but not in the subgroup analyses in the aviptadil or remdesivir cohorts.

Descriptive statistics will be reported overall and by randomized group. For categorical outcomes, the number and percent in each category will be reported; percentages will be of non-missing values, if data are not complete. Continuous variables will be summarized by median (interquartile range [IQR]) and/or mean (SD). Continuous variables may be categorized (e.g., age may be broken into categories to investigate the distribution across age groups).

Stratification: Tests comparing the investigational agent versus control for primary outcomes and key secondary outcomes will be stratified by disease severity (2 strata, by receipt of *invasive mechanical ventilation or ECMO* versus neither).

There are several exceptions:

- Early in the trial, analyses will be unstratified, until sufficiently many participants are enrolled such that each of the two disease severity strata contains at least 20 participants. This guideline on the minimal size of the strata aims to avoid unstable analyses and/or loss of power that may result from the use of sparse strata. In the case of time-to-event data, analyses will be stratified when sufficiently many events have accrued, e.g., at least 10 events per stratum.

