- Sensitivity analyses exploring the effect of stratification will be provided for key analyses that may prompt the DSMB to recommend stopping or modifying the trial. In particular, extensive sensitivity analyses will be provided for the treatment difference in *mortality*, when test statistics approach the interim monitoring boundaries. Such sensitivity analyses will include the following:
 - Unstratified analyses
 - Stratification by study design stratum (3 strata in the aviptadil cohort, 2 strata in the remdesivir cohort)
 - Stratification by disease severity and study design stratum (6 strata in the aviptadil cohort, or 4 in the remdesivir cohort)
 - Additional stratification by geographical region (U.S, Europe, other), provided individual strata are sufficiently large (20 participants or more).

For time-to-event analyses, stratification by disease severity usually implies separate baseline hazard functions for the two strata; if event numbers in strata are too small, however, the strata indicator may be included in the model as an additive covariate instead.

Comment: Randomization in TESICO will be stratified by disease severity, by study site pharmacy, and by the four design strata. The randomization strata were designed to ensure balanced treatment groups. Statistical analyses (treatment comparisons) will be stratified by disease severity only (unless specified otherwise), in order to avoid potentially unstable analyses due to small strata.

For **binary outcomes**, probabilities will be compared between the investigational agent and its control group using Cochran-Mantel-Haenszel tests (CMH) or logistic regression. The CMH tests will be stratified by disease severity, as described above under “stratification”. Odds ratios (OR) with 2-sided 95% confidence intervals (CI) will be estimated using logistic regression models.

For longitudinally measured binary outcomes, the treatment effect through follow-up will be estimated with 95% confidence intervals using generalized estimating equations (GEE) with a logit link function; the treatment effect is estimated via the interaction between the indicator for treatment group and the indicator for follow-up (versus baseline) visits. When there is more than one follow-up visit, “visit number” (day) may be included as categorical variable in the model, for variance reduction; alternatively, “time” may be included as a continuous variable.

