Ordered categorical outcomes (e.g., recovery) will be compared between treatment groups using proportional odds models, and the summary OR will be estimated with a 2-sided 95% CI.² Additionally, to aid the interpretation, the ordinal outcome will be dichotomized according to cumulative probabilities of the ordered categories, comparing treatment groups for proportions of participants in category 1, in the “best 2 categories”, “best 3 categories”, etc.; these comparisons will be performed using logistic regression (or stratified CMH tests).

Models will be adjusted for disease severity at study entry (2 categories, by use of *invasive mechanical ventilation or ECMO* versus neither), by including the corresponding indicator variable in the model.

The validity of the proportional odds assumption will be assessed by testing for heterogeneity in the log ORs (for the treatment effect) across the dichotomized cumulative ordered categories in the corresponding logistic regression model (partial proportional odds model, test for “unequal slopes”).

- The primary sensitivity analysis testing the proportional odds assumption will compare the unadjusted proportional odds model for the treatment comparison (null model) versus a partial proportional odds model that allows for “unequal slopes” across the dichotomized cumulative categories (i.e., when testing the proportional odds assumption for the treatment comparison with respect to the recovery outcome on a given day, the model will allow for heterogeneous ORs across the outcome categories) as well as across the stratification covariate (i.e., the strata defined by disease severity) (full partial proportional odds model).

Continuous outcomes will be compared between treatment groups using ANCOVA models for comparing means, if the ANCOVA model assumptions hold. If the distributions of the continuous outcomes are skewed, outcomes may be transformed, or compared between treatment groups using rank-based methods, such as the Wilcoxon test, or quantile (median) regression. For example, biomarker levels often require log-transformation to meet model assumptions for ANCOVA analyses.

Comparisons between treatment groups for a continuous outcome will be adjusted for baseline values of the outcome, for the purpose of variance reduction, unless there are

concerns over model stability with such an adjustment. For this purpose, the baseline value will be included as covariate in the model (e.g., ANCOVA, linear mixed models).

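### Hospital-free days: SAP section 8.4 calls for comparisons stratified by severity, but the rank test it names is the plain Wilcoxon and no stratified form is specified

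*SAP*

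**What the plan says.** The lead-in to SAP section 8.4 sets a rule for all the outcomes below it: "For each outcome, the treatment groups will be compared by intention-to-treat, stratified by disease severity at study entry", with a pointer to the stratification rules in section 3. The hospital-free days bullet assigns deaths a value of -1, reports medians by group, and says the analysis will "test the hypothesis of no difference between arms with a Wilcoxon rank sum test". It does not say whether that test is stratified.

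Three parts of section 3 bear on this.

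- The stratification paragraph is narrower than 8.4: "Tests comparing the investigational agent versus control for primary outcomes and key secondary outcomes will be stratified by disease severity". Hospital-free days is neither a primary nor a key secondary outcome. A later comment in section 3 nevertheless makes severity the default stratifier for treatment comparisons unless something else is specified.
- Stratification is held back until "each of the two disease severity strata contains at least 20 participants", a limit that "aims to avoid unstable analyses and/or loss of power that may result from the use of sparse strata".
- For skewed continuous outcomes the rank methods offered are "such as the Wilcoxon test, or quantile (median) regression". No stratified rank test is named.

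Section 6 follows the same pattern: its list of methods pairs a stratified CMH test with a Wilcoxon rank-sum test that carries no stratification.

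**The concern.** For most other outcome types the SAP says how severity enters: a stratified CMH test for binary outcomes, a severity indicator in the proportional odds model, and stratified log-rank and Cox analyses for death. The rank test has no such statement. The stratified extension of the Wilcoxon test is a different statistic and needs stated weights, so the 8.4 lead-in alone does not tell a programmer what to run.

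Two things are at stake. If the test is run as named, it discards a factor on which randomisation was stratified. The pooled rank variance then contains between-severity variation that the balanced allocation has already removed from the treatment contrast, so the test is conservative whenever severity predicts the outcome. If the test is stratified instead, the weights would have to be chosen outside the plan, and that choice can move power by several points.

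**Working it through.** **The plan's own figure.** The SAP gives no sample size or power for hospital-free days. Its one stated figure is 640 participants per comparison for the primary ordinal endpoint (OR 1.5, 80% power, two-sided 0.05; section 1.4). The proportional odds formula is

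N = 12 (z₀.₉₇₅ + z₀.₈₀)² / [(ln 1.5)² (1 − Σp³)] = 572.9 / (1 − Σp³).

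Reaching 640 needs Σp³ = 1 − 572.9/640 = 0.105. Six equal categories give 589, and illustrative distributions with 25% to 45% deaths give 609 to 638. So 640 is plausible but cannot be checked exactly, because the supplied text does not contain the category proportions. It is used below only as the planned size.

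**The tests.** With U the rank sum in the active arm, m the size of that arm and r the midranks:

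- Plain Wilcoxon: Z = (U − E)/√V, with E = m(N+1)/2 and V = [m(N−m)/(N(N−1))] Σ(r − r̄)², computed on the whole sample.
- Stratified: Z = Σ w_k(U_k − E_k) / √(Σ w_k² V_k), with ranks taken within severity stratum k. Van Elteren uses w_k = 1/(n_k + 1); an unweighted sum uses w_k = 1.

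**Simulation inputs.** From the SAP: N = 640, 1:1 allocation, two severity strata, deaths scored −1, two-sided 0.05. The OR of 1.5 is borrowed from the primary endpoint. Assumed, because the documents give no values: severe share 20%, 35% or 50%; severity log-odds shift 0, 0.7 or 1.4; in non-severe controls 25% deaths and 12% at zero days, with the rest spread over 1 to 88 days; exact balance within severity. There were 4,000 trials per setting. The simulation standard error is about 0.6 points for power and 0.35 for type I error.

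| Severity shift | Severe share | Power, plain (%) | Power, van Elteren (%) | Gain (points) | Type I error, plain / van Elteren (%) |
|---|---|---|---|---|---|
| 0 | 20% | 83.2 | 83.2 | 0.0 | 5.2 / 5.3 |
| 0 | 35% | 84.0 | 84.0 | 0.0 | 5.0 / 5.0 |
| 0 | 50% | 82.7 | 82.8 | 0.1 | 4.6 / 4.7 |
| 0.7 | 20% | 81.8 | 82.6 | 0.8 | 4.8 / 5.2 |
| 0.7 | 35% | 81.8 | 83.0 | 1.2 | 4.4 / 4.4 |
| 0.7 | 50% | 81.1 | 82.7 | 1.6 | 4.5 / 5.0 |
| 1.4 | 20% | 79.4 | 82.4 | 3.0 | 4.3 / 5.4 |
| 1.4 | 35% | 77.3 | 81.7 | 4.4 | 3.9 / 5.0 |
| 1.4 | 50% | 75.5 | 80.8 | 5.3 | 3.9 / 5.3 |

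**Reading the shift as mortality.** Assumed mortality of 30% versus 50% is a shift of ln(0.5/0.5) − ln(0.3/0.7) = 0.85. A run at that shift (6,000 trials) gave 81.2% to 82.9% with a 30% severe share and 79.4% to 81.1% with a 50% share: 1.7 points each, with plain-test size 4.7% and 4.4%. Assumed mortality of 25% versus 55% is a shift of ln(0.55/0.45) − ln(0.25/0.75) = 1.30. A run there gave 77.1% to 79.8% and 75.9% to 80.9%, gains of 2.7 and 5.0 points. A separate run at 1.4 gave gains of 4 to 6 points.

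**Why the weights matter.** With 20% severe and a non-prognostic stratum, the unweighted sum had 77.2% power against 83.2% for both the plain and van Elteren tests. Its performance also depends on where the effect lies. With 20% severe and a shift of 1.0, ORs of 1.1 (non-severe) and 1.8 (severe) gave 26.0% plain, 27.6% van Elteren and 11.9% unweighted. With the ORs reversed, the figures were 93.7%, 94.4% and 96.4%.

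**Small samples.** At N = 80 with OR 2.5 and a non-prognostic stratum, van Elteren was level or slightly lower: 63.0% to 62.7% with 25% severe (80 × 0.25 = 20, exactly the section 3 minimum) and 62.7% to 61.8% with 50% severe. These differences are about the size of the simulation error, √(0.63 × 0.37/4000) = 0.8 points.

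**The case against.** A reader might infer that the SAP has decided against stratifying this outcome, and so contradicts itself. The text does not support that. No exemption is written, the 8.4 lead-in covers this bullet, the bullets are introduced as short descriptions, and section 3 makes severity the default. Other 8.4 bullets, such as time to sustained recovery, also name a test without repeating that it is stratified. On a charitable reading, a severity-stratified rank test is already intended.

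That stands as a reading of intent, but it does not supply a test. For the competing-risk outcomes, section 8.3 states that the time-to-recovery comparisons are stratified, and the reference list includes a methods paper on stratified competing-risks regression. The rank test has no counterpart, and the narrower wording of the section 3 stratification paragraph leaves room for a plain test.

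It is also fair to say that little hangs on this. Hospital-free days is outside the four key secondary outcomes, no power is claimed for it, the stopping boundaries use mortality, and the plain test is valid. These points limit the importance; they do not settle which test will be run.

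**Conclusion.** The point holds as a gap in specification: 8.4 calls for stratification by severity, the named test does not provide it, and no stratified rank test is defined. The cost of running the plain test runs from nothing to about 6 points of power, as assumed prognostic strength rises from none to a log-odds shift of about 1.4. Plain-test size in the tabulated runs was 3.9% to 5.2%, so the error is conservative.

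Two stronger inferences fail. The first is that a moderate gap, such as 30% versus 50% mortality, costs five points or more. At that gap the gain is about 1 to 2 points, and the documents offer no severity-specific rates that would support a stronger effect. The second is that stratifying is always more powerful and free. The gain needs severity to be prognostic, it depends on the weights, and section 3 itself names a cost with sparse strata.

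The figures rest on a common OR of 1.5 on this scale and exact balance by severity; the heterogeneous-effect runs under the working are the exception to the common OR. The planned urn randomisation within pharmacy strata would give only approximate balance.

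**What to change.** In section 8.4, replace the test for hospital-free days with: *van Elteren test (weights 1/(n+1), n being the stratum size) stratified by disease severity (invasive mechanical ventilation or ECMO vs neither); unstratified Wilcoxon if either stratum has fewer than 20 participants.* The fallback carries over the section 3 minimum and deals with small interim analyses.

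Optionally, report beside the medians a summary odds ratio with 95% CI from a proportional odds model with the severity indicator, since the medians and a p-value give no effect estimate with an interval.

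The cost is one line of SAP text, with no extra data or participants. Section 1.1 already provides for an update by the blinded statisticians before unblinding, and the change should be made then.
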